11.2.4 Outcome

The clinical outcome of an AE will be characterized as follows:

- Resolved without sequelae
- Resolved with sequelae (specify)
- Ongoing (i.e. continuing at time of study discontinuation)
- Death.

11.2.5 Treatment or Action Taken

- None
- Medical Intervention
- Surgical Intervention
- Other.

11.3 ANTICIPATED ADVERSE EVENTS

Adverse events that are anticipated to occur during the study are listed below.

- Death;
- stroke/CVA, TIA or seizure;
- vessel damage, dissection, occlusion, aneurysm, perforation, Post-Procedure neck pain, guidewire perforation, rupture or injury;

- damage to, fracture, fragmentation, or dislocation of the implanted device;
- embolization of air, thrombus, or other embolic debris;
- end organ ischemia, vessel thrombosis, or spasm;
- hypotension/hypertension (acute/subacute to 30 days);
- hypotension/hypertension (chronic>30 days);
- hypertension recurrent;
- infection (local or systemic);
- myocardial infarction;
- puncture site complications (i.e. vessel occlusion, hemorrhage; hematoma, pseudoaneurysm or arteriovenous fistula, excessive blood loss);
- renal insufficiency, kidney failure, hematuria;
- bleeding complications;
- bradycardia or arrhythmias including ventricular fibrillation or tachycardia;
- unintentional detachment or implantation of a component of the system, inappropriate sizing of the device;
- drug reaction;
- allergic reaction to contrast media, medications or device materials; and
- emergent surgery.

11.4 SERIOUS ADVERSE EVENT AND UNANTICIPATED ADVERSE DEVICE EFFECT REPORTING

Serious Adverse Events (SAE) and unanticipated adverse device effects (UADE) must be reported to the study sponsor as soon as possible and no later than 2 days after the investigator first learns of the event.

For initial reports, investigators should record all case details that can be gathered within the reporting timeframe. The contact information for Vascular Dynamics Inc. is below:

VASCULAR DYNAMICS, INC.
[name]
[name]
[name]
[contact]
[contact]
[contact]

Relevant follow-up information should be submitted to Vascular Dynamics, Inc. as soon as it becomes available and/or upon request. For some events, the sponsor or its designee or the medical monitor may follow up with the site by telephone, fax, electronic mail, and/or a monitoring visit to obtain additional case details deemed necessary to appropriately evaluate the event (e.g., hospital discharge summary, consultant report, or autopsy report). Reports relating to the subject's subsequent medical course must be submitted to the study sponsor

until the event has subsided or, in case of permanent impairment, until the event stabilizes and the overall clinical outcome has been ascertained.

11.5 INDEPENDENT ADJUDICATION OF CLINICAL OUTCOME EVENTS BY DSMB

All SAEs and UADEs will be reviewed and adjudicated by the DSMB. Clinical event summaries and relevant imaging studies will be reviewed by the DSMB, which includes an interventional cardiologist, a neurologist, an internist, and a biostatistician.

12.0 ETHICS AND REGULATORY CONSIDERATIONS

12.1 SUBJECT INFORMATION AND CONSENT PROCEDURES

The Investigator, or designee, will obtain written informed consent from the subject prior to performing study assessments. The subject will be informed that the Sponsor and regulatory authorities will have access to personally identifiable information for the purposes of monitoring data against source documentation. However, all data entered in the database, filed, and presented by the Sponsor will be in anonymous form.

The site-customized ICF (see sample ICF provided by Sponsor), must be approved by Vascular Dynamics, Inc. and the IRB/EC before use. Each investigational Site will provide Vascular Dynamics, Inc. with a copy of the IRB/EC approved ICF and renewed approvals and consents as appropriate for the duration of the study.

The original, signed and dated ICF should be retained in the subject's study records, and a copy provided to the subject. The consent completion will be monitored by the Sponsor or designee.

12.2 IRB/EC APPROVAL

The Investigator, or designee, is responsible for submitting the clinical protocol and any amendments to the IRB/EC for approval prior to any subject being enrolled and for obtaining renewals at periods determined by the IRB/EC for the duration of the study.

13.0 STATISTICAL METHODS

Since this is a pilot study designed to evaluate the initial safety of the MobiusHD in subjects with stage 2 hypertension, no formal hypothesis testing is planned. Complete data for each study subject will be presented in an individual patient profile consisting of all CRF fields and a narrative summary. Additionally, where appropriate, descriptive statistics will be used to tabulate and summarize study outcomes. Background and demographic characteristics will be presented. Continuous variables will be summarized by descriptive statistics (sample size, mean and standard deviation, median, minimum and maximum). Discrete variables will be summarized by frequencies and percentages. Adverse events will be summarized by presenting the number and percentage of patients having any adverse event. Any other information collected (such as severity or relationship to study device) will be listed as appropriate. Any statistical tests performed to explore the data will be used only to highlight any interesting comparisons that may warrant further consideration.

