If the Investigator is unable to place a MobiusHD implant in a subject, the subject will be followed to the 30-Day visit and will then be exited from the study in the absence of any ongoing adverse events. If an adverse event is ongoing or not stabilized, the subject will continue to be followed until complete resolution or stabilization of the AE with no expectation or need for further treatment. The reason(s) for failure to place the implant will be documented on the Procedure CRF.

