8.2 STUDY ENROLLMENT

The number of subjects to be enrolled in the study is up to 20. This sample size is estimated to be sufficient to yield acceptable, first-in-man, safety and effectiveness data for initial analysis and to support future regulatory submissions. It is anticipated that up to ten (10) centers inside the United States will be needed to enroll this study in a timely fashion. Each investigational site will be expected to enroll at least two (2) and up to eight (8) subjects.

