9.0 STUDY COMPLETION

After the subject has completed the 3-Year follow-up visit, a Subject Termination iCRF must be completed. During the course of the study, it is possible that subjects will be withdrawn from the study early. Factors leading to subject withdrawal may include, but are not limited to, the following:

- **Subject Withdrawal** - A subject may voluntarily withdraw from the study at any time without affecting his or her future medical treatment or benefits. In addition, the Investigator may withdraw a subject from the study if the subject refuses further testing or follow-up evaluations, or for any other reason as determined by the Investigator.
- **Subject Lost to Follow-Up** – If the Investigator has attempted to contact a subject at least three (3) times and receives no response, the subject may be lost to follow-up. The research staff should document at minimum three (3) attempts to contact the subject prior to terminating the subject from the trial.
- **Subject Death** - When a subject expires, the Serious Adverse Event and Subject Termination iCRFs must be completed promptly. Source documents such as death summary, autopsy report (if done), and a copy of the death certificate should be redacted of personal identifiers and provided to the designated clinical monitor and DSMB to describe the cause of the subject's death. The Investigator will notify the IRB/EC and Sponsor within 24 hours of learning of the event.

The Termination iCRF should be completed for each study subject, to record date and reason for early termination (if subject does not complete the study) or at the final visit (if subject completes all study time points).

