11.0 ADVERSE EVENTS

Safety assessments include adverse events and serious adverse events. The reporting period is from the initial treatment through the last study visit (Month 36).

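### Section 13.0 summarises adverse events in aggregate only as a percentage of patients, with no account of observed time, so the 12-to-36-month figures would be biased low if event-free leavers stay in the denominator

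*Combined protocol and SAP*

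**What the plan says.** Section 13.0 describes a pilot in which "no formal hypothesis testing is planned". Its aggregate adverse event (AE) summary is one sentence: "Adverse events will be summarized by presenting the number and percentage of patients having any adverse event". Severity, relationship and similar items are to be listed as appropriate. The section names no denominator for any period, no person-time rate, no time-to-event estimate and no handling of incomplete follow-up.

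The same section also commits to subject-level output: "Complete data for each study subject will be presented in an individual patient profile consisting of all CRF fields and a narrative summary".

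Other sections set the time frame and the routes of exit:

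- Section 11.0 on AEs: "The reporting period is from the initial treatment through the last study visit (Month 36".
- The synopsis sets the primary safety outcome at six months from implantation and lists one-to-three-year safety among the additional outcomes.
- Section 9.0 says "it is possible that subjects will be withdrawn from the study early". It names withdrawal, loss to follow-up and death, and has the termination form record the date and reason.
- Section 22.0 allows removal for non-compliance, an SAE or another medical condition.
- Section 7.0, for a subject in whom no implant can be placed and who has no ongoing AE: "the subject will be followed to the 30-Day visit and will then be exited from the study".
- Section 11.2 has every subject exposed to study treatment evaluated for AEs.
- Section 8.2: "The number of subjects to be enrolled in the study is up to 20". They are planned as ten unilateral, then ten bilateral.

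**The concern.** A percentage of patients with an event treats everyone in the denominator as observed for the whole period. Over 36 months with possible exits, that need not be so. Section 11.2 makes all treated subjects the natural denominator. On that reading, a subject who leaves event-free at Month 6 counts as having no event at Month 36, although 30 of the 36 months were never observed.

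At stake is the description of later safety for a permanent carotid implant. Section 8.2 intends these data to support later regulatory submissions. The unilateral and bilateral cohorts are likely to be read side by side. If they differ in drop-out, their crude percentages are not like for like, and one subject is a tenth of a cohort of ten.

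**Working it through.** The documents state no event rate, drop-out rate or precision target, so there is no figure of the plan's to reproduce. The rates below are assumptions, chosen to show the size and direction of the effect.

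**Inputs.** From the documents: 36 months (3 years) of reporting and up to 20 subjects. Assumed: true 36-month incidence of a first event p = 30%; annual loss a = 0 to 15%; drop-out independent of event risk.

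**Constant hazard, all treated in the denominator.** Let λ = −ln(1 − p)/3 = 0.1189 per year and μ = −ln(1 − a). The expected crude proportion is λ/(λ + μ) × [1 − exp(−3(λ + μ))]. At a = 10%, μ = 0.1054, so 0.1189/0.2243 × [1 − exp(−0.6728)] = 0.530 × 0.490 = 26.0%.

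**Early-clustered events, all treated in the denominator.** Suppose 80% of first events are spread evenly over months 0 to 6 and 20% over months 6 to 36. The expected crude proportion is p × [0.8 A(0, 0.5) + 0.2 A(0.5, 3)], where A(s, t) = [exp(−μs) − exp(−μt)]/[μ(t − s)]. At a = 10%: 0.30 × [0.8 × 0.974 + 0.2 × 0.834] = 28.4%.

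**Constant hazard, only subjects with an event or 36 completed months in the denominator.** The expected value is crude/[crude + exp(−3(λ + μ))]. At a = 10%: 0.260/(0.260 + 0.510) = 33.7%.

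| Annual loss | Drop-out risk by Month 36, 1 − (1 − a)³ | All treated, constant hazard (shortfall, points) | All treated, 80% of events by month 6 (shortfall, points) | Event or completed, constant hazard |
|---|---|---|---|---|
| 0% | 0% | 30.0% (0) | 30.0% (0) | 30.0% |
| 5% | 14.3% | 27.9% (2.1) | 29.2% (0.8) | 31.8% |
| 8% | 22.1% | 26.7% (3.3) | 28.7% (1.3) | 32.9% |
| 10% | 27.1% | 26.0% (4.0) | 28.4% (1.6) | 33.7% |
| 15% | 38.6% | 24.1% (5.9) | 27.6% (2.4) | 35.9% |

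Across 5 to 15% annual loss, the all-treated shortfall is 0.4 to 1.2 subjects of 20 under the constant hazard and 0.2 to 0.5 with early clustering.

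**Earlier time points.** The same λ, with 1 or 2 years in place of 3, gives a true incidence of 11.2% at 12 months and 21.2% at 24 months. The shortfalls for 5 to 15% annual loss are 0.3 to 0.8 and 1.0 to 3.0 points.

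**Six-month primary window.** If the true six-month incidence were 30% with a constant hazard (λ = −ln(0.7)/0.5), the crude value would be 29.6%, 29.3% and 28.9% at 5, 10 and 15% annual loss. The shortfall is at most about 1.1 points.

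**How the alternative works.** Take a constructed set of 20 with events at months 1, 5, 14, 20, 28 and 33 and event-free exits at months 2, 6, 9, 12 and 15. The crude figure is 6/20 = 30%. Kaplan-Meier gives 1 − (19/20 × 17/18 × 13/14 × 11/12 × 10/11 × 9/10) = 37.5%. This set is deliberately severe, with a quarter of subjects gone by month 15 and four of six events after month 12. It shows the mechanism and does not forecast this trial.

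**The case against.** Several stronger readings are tempting, and the documents do not support them.

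- *The percentage is all the reader will get.* Section 13.0 also promises a complete profile and narrative for every subject, and exit dates are recorded. With at most 20 subjects, observation time can be recovered by hand. What remains is that the tabulated figure makes no use of it.
- *The plan counts leavers as event-free, so its figures are biased low.* No sentence says so, because no denominator is stated. The last column of the table shows that another ordinary choice biases upward. A subject removed because of an SAE already counts as an event. The downward bias is conditional on an all-treated denominator and on some event-free exits.
- *Early exits are expected.* Section 9.0 calls them possible and gives no rate.
- *Day-30 exits dilute the implant's long-term figures.* Those subjects received no implant. Whether they belong in the denominator is an analysis-population question. Censoring them at Day 30 alongside implanted subjects would credit them with a later hazard from a device that they do not carry.

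Two further objections have weight. Many of the anticipated events in Section 11.3 are procedural, so clustering of events soon after implantation is plausible, and the smaller shortfalls may be nearer the truth. And in a descriptive pilot, imprecision dominates: the exact 95% interval for 6/20 is 11.9% to 54.3%. Kaplan-Meier also needs non-informative censoring, and Section 22.0 allows removal for medical reasons.

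These points limit the size of the concern. They do not supply the missing denominator or the missing account of follow-up time. Death is not a competing risk for first SAE, because Section 11.1.1 makes an AE that results in death an SAE.

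**Conclusion.** The point holds in conditional form, as a minor but worthwhile improvement. The one aggregate AE measure takes no account of observed time over a period of up to 36 months in which early exit is foreseen. With all treated subjects in the denominator and some event-free leavers, the 12-to-36-month percentages are biased low. The shortfall at Month 36 is about 2 to 6 points under a constant hazard and about 1 to 2 points with 80% of events by month 6, assuming a true 30% and 5 to 15% annual loss. It is zero without drop-out. The six-month primary outcome is little affected. All the rates are assumptions, and the drop-out is taken as independent of event risk.

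**What to change.** In Section 13.0, keep n/N with its denominator stated, and add for implanted subjects, overall and by unilateral and bilateral cohort:

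- the number still under observation at 6, 12, 24 and 36 months;
- the Kaplan-Meier cumulative incidence of first SAE at the same times, censored at last contact;
- the number of SAEs per subject-year actually observed.

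Report subjects without an implant separately, through their exit from the study.

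The cost is a few sentences and one table. The termination form already records exit dates, and Section 11.2 has AEs evaluated from onset. The sample forms are not reproduced, so it should be confirmed that the onset date is a recorded field. The downside is that late estimates will look slightly less favourable, will be imprecise with ten subjects per cohort, and will rest on non-informative censoring. The table should say so and be read beside the recorded reasons for exit.

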14.0 RECORDS AND REPORTS

14.1 RECORDS

The investigational site will maintain iCRF and source study records for monitoring and audit purposes for the latter of:

- At least two (2) years after study completion
- At least two (2) years after Sponsor receives approval from the local governing regulatory authority
- For the period required by the local governing authority and reviewing IRB/EC

Sponsor is to be advised prior to destruction of study records and notified if study records are moved to an off-site location for archiving.

14.2 REPORTS

Investigators at participating sites are required to submit reports in conformance with all applicable regulations.

15.0 DATA MANAGEMENT

All required data for this study will be collected on appropriate source medical records and study forms and entered into a secure, 21 CFR Part 11 compliant, web-based database (MedNet Solutions, Inc.).

16.0 MONITORING OF THE STUDY AND QUALITY CONTROL

16.1 DSMB

All SAEs will be evaluated by the DSMB for potential relationship to the investigational device or procedure. All AEs will be evaluated by Sponsor for significance and relevance with respect to trends that may represent a previously unknown or unanticipated risk that may relate to the investigational device or procedure.

16.2 DATA COLLECTION AND MONITORING

The Research Coordinator will collect and document data in hospital and clinic charts and on source document forms prepared for the study. iCRF data will be entered in anonymous form into the secure web-based, password protected database. Passwords will not be issued by the Sponsor until Site Initiation and database training has been conducted for all personnel to whom Investigator has delegated data entry responsibilities. Hardcopy blank CRFs may be reproduced as needed and may be used as source documents; these should be signed and dated by the person collecting the data. Completed iCRFs in final form (with queries resolved) may be printed and filed in hardcopy for archiving if required by local governing authority. All data will be exported and stored on appropriate electronic media by Sponsor and to biostatistician for analysis.

The Sponsor will designate and train monitors to review iCRF data against source documents for completeness and accuracy. Discrepant data will be queried; the electronic

database will maintain audit trails of all queried and corrected data. The Investigator is responsible for data integrity at the site and will review and electronically sign all Inclusion/Exclusion, Adverse Event, Deviation, and Terminations iCRFs.

16.3 SOURCE DOCUMENTATION

Regulations require that Investigators maintain information in the study subject's medical records that corroborate data reported in the iCRFs. In order to comply with these regulatory requirements, at a minimum, the following information should be maintained:

- Sufficient medical history/physical condition of the study subject before involvement in the study to verify protocol entry criteria;
- Dated and signed notes on the day of entry into the study including a statement regarding the consent process that was followed;
- A log that maps the key to subject identity for monitors and auditors showing subject name and assigned identification number. This record will not be collected by Sponsor but should be maintained at the study site so that the appropriate medical records are compared to study iCRF data;
- Dated and signed progress notes, procedure reports, assessments, and diagnostic results as appropriate to each study subject visit to confirm iCRF data;
- Investigator / site radiologist assessment of medical imaging;
- Evaluate clinical significance of abnormal lab results;
- Records following adverse events reported, results of diagnostic tests ordered, treatment given, and clinical outcome at resolution or stabilization;
- Dictated procedure report;
- Dictated discharge summary;
- Notes regarding medications taken during the study; and
- Study subject's condition upon completion of, or withdrawal from, the study.

16.4 SITE COMPLIANCE / DEVIATIONS

The clinical site will be monitored routinely for adequate enrollment, timeliness of data submission, and compliance with the Investigational Plan and local regulations. Consistent pattern of non-compliance with respect to the above will require a corrective action plan to be negotiated with the Investigator. If corrective actions are not effective in resolving site compliance, the Sponsor may withdraw the clinical site from the study.

Significant deviation from the protocol will be reported to the Sponsor via the Deviation iCRF which may be completed by the site or the Sponsor. The Sponsor will categorize and report deviations (e.g., improper informed consent, inappropriate use of investigational device, visit outside window, assessment missed).

In the event that the Investigator identifies a potential subject that meets all but one (1) Inclusion/Exclusion criterion and expresses a medical opinion regarding why it is appropriate to consider the patient for the study, this documentation may be submitted to the

Sponsor for consideration. If the Sponsor agrees, then a prospective deviation may be approved to allow the subject to be enrolled in the study.

16.5 MONITORING PLAN

Study monitoring activities will include Site Initiation Visits, interim Site Monitoring Visits and a Site Close-Out Visit.

- The Site Initiation Visit enables the Sponsor to thoroughly review the study protocol and CRFs with the Investigator's staff, in order to assure that the Investigator understands the Protocol. This includes (1) assessing required records and reports; (2) verifying the staff has sufficient background, facilities, subject load, time, and willingness to comply with the study requirements; is able to submit the Protocol to the IRB/EC for review and approval; and can maintain all correspondence, the Protocol, and all required records on file; and (3) verifying that the Principal Investigator can submit required reports, assumes responsibility for the investigation at his or her institution (which may include supervision of some tasks), and has sufficient experience with the study population.
- Site Monitoring Visits will be scheduled depending on the rate of subject enrollment. During the Site Monitoring Visit, the monitor will review the CRFs of each subject in the study to make certain that the data provided are accurate and obtained in the manner specified in the Protocol. The subjects' clinical records will be reviewed to confirm that the case report form data are consistent with the Investigator's clinical records, the background data and concurrent medication are documented in the CRFs, and that there is an accurate account of the use of the investigational device in the treatment. The Site Study Binder and other study documents will be reviewed. The subjects' clinical records will be reviewed to determine whether recording of adverse events has been omitted in the CRFs. If this is found to be so, the CRFs will be returned to the Investigator and corrected to include this information. During the course of the study, the Sponsor shall be available to discuss, in person or by telephone, questions regarding adverse effects, removal of subjects from the study, conduct of the study, etc.
- At the completion or termination of this study a Site Close-Out Visit will be conducted.

